9.15 Medical Care of Subjects after End of Trial

After a subject has completed the trial or has withdrawn from the study, standard treatment will be administered, if required, in accordance with the trial site's standard of care and generally accepted medical practice and according to the subject's individual medical needs.

10 EFFICACY AND SAFETY VARIABLES

Table 1 summarizes the study required evaluations.

10.1 Efficacy Variables

Radiological and/or physical assessments of the tumor lesions, and evaluations of relevant tumor markers (e.g. CA125, PSA, CA19-9, CA27.29, thyroglobulin, anti-thyroglobulin antibodies, calcitonin and CEA, to be assessed at the judgment of the Investigator) will be made at screening (4 weeks before the first study drug administration), at the end of cycle 2 and at approximately 8 week intervals thereafter until disease progression. Additional tumor assessments may be conducted at the judgment of the Investigator. Subjects who discontinue treatment for reasons other than disease progression must continue tumor assessments until disease progression, withdrawal of their consent to study procedures or initiation of another anticancer therapy. Efficacy assessments may also be conducted at treatment discontinuation (End of Treatment visit) if the reason for the treatment termination is other than disease progression and a tumor assessment was not done within 8 weeks before treatment discontinuation (assessment must be

conducted before additional anti-tumor therapy is started). Scans at the End of Treatment visit will be also conducted if required to confirm response to treatment.

Lesions to be included in the tumor assessments should follow RECIST v1.1. Spiral CT scan with a contrast agent is the preferred imaging method. Tumor assessment with spiral CT scans should be performed as appropriate. Subjects with contrast allergy may use non-contrast CT or MRI, whichever is required to adequately assess all disease.

Objective response (complete response and partial response) as determined by the subject's best tumor response, duration of response, and time to progression will be assessed using RECIST v1.1. Confirmation of response is required.

In addition to Investigator's tumor response assessment, a central independent review tumor response assessment may be performed if the sponsor deems it necessary for the final assessment of the efficacy of the treatment. If an independent radiological review were to be conducted, reviewers will be blinded to the Investigator's efficacy assessments. The sponsor, in consultation with the investigators, may initiate this independent review at any time during the trial. In that case, an independent review committee charter would be generated to provide the specific procedures that would be filed with IRBs/IECs and regulatory authorities prior to their initiation.

Upon disease progression, all subjects will be followed approximately every 12 weeks for survival and the use of subsequent therapy until either death or 12 months after accrual in the subject's study cohort has been completed, whichever occurs first. Information on survival and subsequent anticancer therapy may be collected by phone.

10.2 Assessment of Safety

Adverse events will be graded according to the NCI CTCAE v 4.03. Adverse events will be summarized by relationship to trial drug, severity and grade. The safety profile of the IPs will be assessed through the recording, reporting and analyzing of baseline medical conditions, adverse events, physical examination findings including vital signs and laboratory tests. Comprehensive assessment of any apparent toxicity experienced by the subject will be performed throughout the course of the trial, from the time of the subject's signature of informed consent. Trial site personnel will report any adverse event (AE), whether observed by the Investigator or reported by the subject.

A safety monitoring committee comprised of the Investigators and Sponsor clinicians or designees will review all relevant safety data on a regular basis.

10.3 Adverse Events

An AE is any untoward medical occurrence in a subject or clinical investigation subject administered a pharmaceutical product, which does not necessarily have a causal relationship with this treatment. An AE can therefore be any unfavorable and unintended sign (including an abnormal laboratory finding), symptom, or disease temporally associated with the use of a

medicinal product, whether or not considered related to the medicinal product. In cases of surgical or diagnostic procedures, the condition/illness leading to such a procedure is considered as the AE rather than the procedure itself. In case of a fatality, the cause of death is considered as the AE, and the death is considered as its outcome.

The Investigator is required to grade the severity/intensity of each adverse event. Investigators will reference the NCI-CTCAE v 4.03. This is a descriptive terminology that can be used for adverse event reporting. A general grading (severity/intensity) scale is provided at the beginning of the referenced document, and specific event grades are also provided. If a particular AE's severity/intensity is not specifically graded by the guidance document, the Investigator is to revert to the general definitions of Grade 1 through Grade 5 and use his or her best medical judgment.

The 5 general grades are:

- Grade 1: Mild
- Grade 2: Moderate
- Grade 3: Severe
- Grade 4: Life-threatening or disabling
- Grade 5: Death related to AE. Note: Death (Grade 5 as defined by NCI-CTCAE version 4.03) is mainly regarded as an outcome, to be documented as described below.

According to the Sponsor's convention, if a severity/intensity of Grade 4 or 5 is applied to an AE, then the Investigator must also report the event as a serious adverse event (SAE; see definition below) as per Section 10.5. However, a laboratory abnormality with a severity/intensity of Grade 4, such as anemia or neutropenia, is considered serious only if the condition meets one of the serious criteria described below.

In the case of death, the primary cause of death (the event leading to death) should be recorded and reported as an SAE. "Fatal" will be recorded as the outcome of this respective event; death will not be recorded as separate event. Only if no cause of death can be reported (e.g., sudden death, unexplained death), the death per se might be reported as an SAE.

Investigators must also systematically assess the causal relationship of AEs to the IPs, other medicinal products using the following definitions. Decisive factors for the assessment of causal relationship of an AE to the trial treatments include, but may not be limited to, temporal relationship between the AE and the trial treatments, known side effects of the trial treatments, medical history, concomitant medications and procedures, course of the underlying disease, trial procedures.

Relatedness of an AE will be evaluated as follows:

- Not related: Not suspected to be reasonably related to the IPs. AE could not medically (pharmacologically/clinically) be attributed to the IPs under trial in this clinical trial protocol. A reasonable alternative explanation must be available.
- Related: Suspected to be reasonably related to the IPs. AE could medically (pharmacologically/clinically) be attributed to the IPs under trial in this clinical trial protocol.

10.4 Abnormal Laboratory Findings and Other Abnormal Investigational Findings

Abnormal laboratory findings and other abnormal investigational findings (e.g. on an ECG trace) should not be reported as AEs unless they are associated with clinical signs and symptoms, lead to treatment discontinuation or are considered otherwise medically important by the Investigator. If an abnormality fulfills these criteria, the identified medical condition (e.g. anemia, increased ALT) must be reported as the AE rather than the abnormal value itself.

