9.5 Dose Modification and Management of Toxicity

All subjects will begin treatment with tipifarnib at a starting dose of 600 mg bid in alternating weeks. If treatment-related, treatment-emergent AEs are observed meeting criteria for dose modification detailed further in this section, the dose level reductions summarized in Table 2 will be used.

Table 2: Tipifarnib dose levels

Dose Level	Alternate Week Schedule	
	Doses in mg (am + pm)	
Starting Dose	600 + 600	
-1	300 + 600*	
-2	300 + 300	

^{*}Depending on subject preference, the 600 mg dose may be taken in the morning or in the evening, as long as the total daily dose is 900 mg, i.e. 600 mg can be taken in the morning or evening with 300 mg taken for the other scheduled dose time. Tipifarnib should always be taken with a meal.

If treatment-related treatment-emerging CTCAE grade 4 non-hematological toxicity is observed, treatment with tipifarnib will be permanently discontinued.

If treatment-related treatment-emerging CTCAE \geq grade 3 hematological or grade 3 non-hematological toxicity is observed that cannot be managed with supportive care measures, treatment with tipifarnib will be interrupted until recovery to \leq grade 2. If recovery requires more than 4 weeks, treatment is to be discontinued. Upon recovery, tipifarnib may be restarted at the original dose or at the next lower dose level (see Table 2) at the discretion of the investigator. If grade 3 or 4 toxicity recurs, subsequent dose reductions may be conducted according to Table 2.

If treatment-related treatment-emerging CTCAE grade 2 renal toxicity is observed that cannot be managed with supportive care measures (including hydration and correction of electrolyte abnormalities, if appropriate), treatment with tipifarnib will be interrupted until recovery to \leq grade 1. Upon recovery to \leq grade 1, the subject may restart tipifarnib at their current dose level.

If treatment-related treatment-emerging CTCAE grade 2 renal toxicity recurs or if grade 3 renal toxicity is observed that cannot be managed with supportive care measures, treatment with tipifarnib will be interrupted until recovery to \leq grade 1. Additional treatment may be given at the next lower dose level (see Table 2) upon subject's recovery from toxicity. If grade 2 or 3 renal toxicity recurs, a subsequent dose reduction may be conducted. Reduced doses due to renal toxicity will not be re-escalated.

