Treatment with tipifarnib should also be interrupted until recovery to grade 2 tolerable or better if treatment-related treatment-emergent CTCAE grade 2 intolerable neurological toxicity is observed. Additional treatment may be given at the next lower dose level (see Table 2) upon subject's recovery from toxicity. If grade 2 intolerable neurological toxicity recurs, a subsequent dose reduction may be conducted. Reduced doses due to neurological toxicity will not be reescalated. The occurrence of grade 3 neurological toxicity will result in permanent discontinuation of treatment.

Unless otherwise indicated (e.g. dosing discontinuation), reduced doses may be re-escalated to the original dose at the judgement of the investigator. However, subjects who experience serious adverse events or a recurrence of \geq grade 3 toxicity deemed to be related to tipifarnib will not

have their dose re-escalated following dose reduction. In addition, subjects experiencing more than one dose delay of \geq 14 days will not have their dose re-escalated.

Asymptomatic laboratory findings will not be considered dose limiting unless otherwise determined by the Investigator. A summary of dose modifications is presented in Table 3.

Table 3: Summary of Dose Modifications for Treatment Related Toxicities

Adverse Event	Management	Tipifarnib Dosing
Grade 4 Non-Hematological	Discontinue tipifarnib permanently	
≥ Grade 3 Hematological or Grade 3 Non-Hematological	Manage with BSC, including RBC or platelet transfusion. If not manageable, interrupt tipifarnib treatment until recovery to grade 2 or better.	If recovery requires more than 4 weeks, treatment is to be discontinued.
		Upon recovery to ≤ grade 2, restart tipifarnib at current dose or at the next lower dose level (see Table 2) at the judgement of the investigator.
		If the same toxicity recurs, upon recovery to ≤ grade 2, re-start tipifarnib at the next lower dose level (see Table 2). If grade 3 thrombocytopenia recurs, consider additional cycles at original dose at the judgement of the investigator
Grade 2 Renal	Manage with BSC, including hydration and correction of electrolyte abnormalities, if appropriate.	Upon recovery to ≤ grade 1, restart tipifarnib at current dose.

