Grade 2 Recurrent or Grade 3 Renal	Manage with BSC, including hydration and correction of electrolyte abnormalities, if appropriate. If not manageable, interrupt tipifarnib treatment until recovery to grade 1 or better	Upon recovery to ≤ grade 1, restart tipifarnib at the next lower dose level (see Table 2). If grade 2 or 3 renal toxicity recurs, upon recovery to ≤ grade 1, re-start tipifarnib at the next lower dose level (see Table 2).
Grade 2 non-tolerable Neurological	Manage with BSC. If not tolerable, interrupt tipifarnib treatment until recovery to grade 2 tolerable or better	Upon recovery to grade 2 tolerable or better, re-start tipifarnib at the next lower dose level (see Table 2).
		If grade 2 intolerable neurological toxicity recurs, upon recovery to grade 2 tolerable or better, re-start tipifarnib at the next lower dose level (see Table 2).
Grade 3 Neurological	Discontinue tipifarnib permanently	

In exceptional circumstances, dosing delays or skipping of dosing for reasons other than the management of toxicity will be allowed at the judgement of the investigator as long as 50% of the total dose is maintained in a given cycle.

Upon restarting tipifarnib following a treatment interruption, the cycle and dosing day are to be defined by the following:

- If a dose delay/interruption occurs and resolves within a cycle, dosing picks up where it left off
 - o For example, if a subject's treatment is held on Day 3, subject recovers 14 days later (nominal Day 17 in the cycle) and resumes tipifarnib treatment, the subject is considered to be dosing on Day 3 of the same cycle.
- If the delay goes beyond the cycle (> nominal day 28 of that cycle), upon recovery, the subject should be started at Day 1 of the next cycle.
 - o For example, if a subject's treatment is held on Day 3, subject recovers 30 days later (nominal Day 33 in the cycle) and resumes tipifarnib treatment, the subject is considered to be dosing on Day 1 of the next cycle.

Radiographic imaging for tumor response must maintain the fixed time schedule and is invariant to the drug exposure of the subject. Radiographic imaging will be performed at least once approximately every 8 weeks for 6 months, thereafter once approximately every 12 weeks. All other procedures/visits can follow the cycle's drug administration.

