10.5 Serious Adverse Event

An SAE is any untoward medical occurrence that at any dose:

- Results in death.
- Is life-threatening. NOTE: The term "life-threatening" in this definition refers to an event in which the subject is at risk of death at the time of the event; it does not refer to an event that hypothetically might cause death if it were more severe.
- Requires inpatient hospitalization or prolongation of existing hospitalization.
- Results in persistent or significant disability/incapacity.
- Is a congenital anomaly/birth defect.
- Is otherwise considered as medically important.

Important medical events that may not result in death, be life-threatening, or require hospitalization may be considered as SAEs when, based upon appropriate medical judgment, they may jeopardize the subject or may require medical or surgical intervention to prevent one of the outcomes listed in this definition. Examples of such events include allergic bronchospasm requiring intensive treatment in an emergency room or at home, blood dyscrasias or convulsions that do not result in subject hospitalization, or the development of drug dependency or drug abuse.

For the purposes of reporting, any suspected transmission of an infectious agent via an IP is also considered a serious adverse reaction and all such cases should be reported in an expedited manner.

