10.8 Methods of Recording and Assessing Adverse Events

At each trial visit, the subject will be queried on changes in his/her condition. During the reporting period of the trial any unfavorable changes in the subject's condition will be recorded as AEs, whether reported by the subject or observed by the Investigator.

Complete, accurate and consistent data on all AEs experienced for the duration of the reporting period (defined below) will be reported on an ongoing basis in the appropriate section of the eCRF. Among these AEs, all serious AEs must be additionally documented and reported using an Adverse Event Report Form. It is important that each AE report include a description of the event, its duration (onset and resolution dates (/times "/times" to be completed when it is important to assess the time of AE onset relative to the recorded treatment administration time)), its severity, its relationship with the trial treatment, any other potential causal factors, any treatment given or other action taken (including dose modification or discontinuation of the IPs) and its outcome. In addition, serious cases should be identified and the appropriate seriousness criteria documented. Specific guidance can be found in the eCRF completion and monitoring conventions provided by the Sponsor.

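### The SAP bases its hematology toxicity summary on reported adverse events and only lists measured grades, so asymptomatic grade 3–4 laboratory values may be missing from the tables, and the change from the protocol is not declared

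*Protocol*

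**What the plan says.** **Reporting rule.** Protocol 10.3 defines an adverse event broadly enough to cover "any unfavorable and unintended sign (including an abnormal laboratory finding"). Protocol 10.4 then narrows what is reported: abnormal laboratory findings "should not be reported as AEs unless they are associated with clinical signs and symptoms, lead to treatment discontinuation or are considered otherwise medically important". Importance is left to the Investigator to judge. No CTCAE grade triggers a report.

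**Protocol analysis plan.** Section 12.2.2 names changes in laboratory results as one of four bases for the safety assessment. It plans the incidence of grade 3 and 4 hematological toxicity by cycle and across cycles, and says that laboratory tests are graded by CTCAE v4.03.

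**SAP.** Section 10 keeps the protocol's vital-sign and ECG items, but its laboratory item covers only hematology and chemistry toxicities that were reported as adverse events. Section 10.2 summarises hematological adverse events of grade 3 or above and promises a similar summary for selected chemistry toxicities. The by-cycle tables of grade 3 or above toxicity sit in section 10.1, under adverse events. Measured chemistry and hematology results, with toxicity grade and clinical assessment, are assigned to listings. Section 14 declares two changes from the protocol: an added overall survival analysis and a PFS/DOR sensitivity analysis in a subset.

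**The concern.** A table built from adverse event records can show only what the reporting rule lets through. For symptomatic toxicity that does no harm. For laboratory toxicity it can, because a severe cytopenia or a creatinine rise may be silent. If it is silent, does not end treatment and is not judged medically important, 10.4 keeps it out of the adverse event data, and the SAP's hematology table then cannot count it.

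This matters for this drug. Protocol 9.4 calls myelosuppression the most common toxicity of the 21-day schedule (45% at 300 mg bid), and it lists hematological events among the most common adverse events seen in this study. Table 1 of the protocol notes creatinine elevation and hypokalemia. Tolerability observations also led to the cut in starting dose from 900 to 600 mg bid, yet the only safety table the SAP splits by starting dose is one of adverse events. A reader of the report would take the grade 3+ hematology table as the rate of severe laboratory toxicity, when it is the rate of reported events.

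**Working it through.** The plan states no figure for this point, so the check traces one case through the text and then counts what has no specified table.

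**1. One case.** Take an asymptomatic grade 3 neutropenia in a subject who stays on treatment.

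| Step | Source | Result |
|---|---|---|
| Can it be an adverse event? | Protocol 10.3 | Yes |
| Signs or symptoms? | Protocol 10.4 | No |
| Led to discontinuation? | Protocol 10.4 | No |
| Judged medically important? | Protocol 10.4 | Left to the Investigator |
| In the hematology toxicity table? | SAP 10.2 | Only if reported as an adverse event |
| In a listing with its grade? | SAP 10.2 | Yes |

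The value is kept, but whether it is tabulated depends on one judgement.

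**2. Protocol against SAP.** Of the four safety items in protocol 12.2.2, the SAP retains adverse events, vital signs and ECG. The fourth, laboratory changes, becomes toxicities reported as adverse events. No table of worst grade, grade shift or change from baseline in measured laboratory values is specified, and section 14 is silent on this.

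**3. Data with no specified table of measured values.** Protocol 10.14.1 lists 10 hematology and 18 chemistry parameters: 10 + 18 = 28. For a subject treated for 12 cycles, protocol 11.3, 11.4 and 11.6 give scheduled post-baseline draws at Cycle 1 Day 7 (1), Day 1 of Cycles 2–12 (11) and End of Treatment (1): 1 + 11 + 1 = 13. This counts data collected, not events lost, and CTCAE does not grade every parameter.

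**4. Size, as an assumption only.** Let t be the true proportion of subjects with grade 3+ laboratory toxicity and f the fraction of them whose toxicity is reported under 10.4. The table then shows t × f. Neither value is in the documents. With t = 30%:

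| f | Shown (30% × f) |
|---|---|
| 0.3 | 9% |
| 0.5 | 15% |
| 0.7 | 21% |
| 0.9 | 27% |
| 1.0 | 30% |

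The relative shortfall is 1 − f, which is zero if Investigators judge every such value medically important.

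**5. Timing of draws, which bears on the remedy.** Dosing is on Days 1–7 and 15–21 of 28. After Cycle 1 Day 7, scheduled on-treatment draws fall on Day 1 of the next cycle (± 2 days), so for a subject dosed on schedule they follow the off-drug Days 22–28. Values from the second dosing week, and from any dosing week after Cycle 1, would often come from unscheduled draws. SAP 7.1 keeps those out of summary tables.

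**The case against.** **Safeguards exist, and they stand.** SAP 10.2 lists each result with its grade, so an omission can be found. SAP 8.4 tabulates dose reductions, interruptions and withdrawals, and SAP 10.3 tabulates transfusions by cycle. At most, the link from an action to a named toxicity is lost.

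**A reader might infer that events leading to a hold, reduction or transfusion go unreported, because 10.4 does not list those actions.** The documents do not support this. Protocol 9.5 applies its dose levels when "treatment-related, treatment-emergent AEs are observed meeting criteria for dose modification", so it starts from an adverse event. It adds: "Asymptomatic laboratory findings will not be considered dose limiting unless otherwise determined by the Investigator". An Investigator who so determines, or who transfuses or interrupts under Table 3, has come close to judging the finding medically important. Protocol 10.5 includes "blood dyscrasias or convulsions that do not result in subject hospitalization" among its examples of important events. Protocol 10.3 discusses when a grade 4 laboratory abnormality is serious, which presupposes that such abnormalities can be reported. The gap is therefore mainly in silent values that prompted no action.

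**A reader might also infer that all laboratory tables rest on adverse events only.** That is firm for hematology but not for chemistry: SAP 10 speaks of similar analyses for chemistry tests, and 10.2 lists test parameters. The table shells, a companion document, could settle it but are not available here.

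**Nor does the SAP 7.1 exclusion of unscheduled measurements show that the present tables are incomplete.** An adverse event found at an unscheduled draw would still be counted. The exclusion matters only for a new table of measured values.

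**Finally, the secondary endpoint is TEAEs and SAEs, not laboratory grades, and nothing shows that 10.4 was applied differently by site or starting dose.** This limits the weight of the point but does not answer it, since protocol 12.2.2 planned a laboratory assessment for which the SAP specifies no table.

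**Conclusion.** The point holds in a limited form. The SAP moves the hematology toxicity summary to reported adverse events, leaves measured grades in listings, and does not declare the departure from protocol 12.2.2. Combined with the 10.4 reporting rule, asymptomatic grade 3–4 values may be missing from the tables.

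The number missing cannot be derived from the documents and may be zero. It depends on how often Investigators judged such values medically important, and on table shells and eCRF conventions that are not in the documents. The conclusion reads SAP 10.2 as taking hematology from adverse event records, as its wording says, and leaves the chemistry source open. Objective response rate is unaffected.

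**What to change.** In SAP 10.2, add a table of the worst post-baseline CTCAE v4.03 grade, with shift from baseline, derived from measured hematology and chemistry values for the parameters that CTCAE grades. Present it by cohort and by starting dose, beside the adverse event tables. Include unscheduled results, as a stated exception to SAP 7.1, for the timing reason in step 5 of the working. Record the change in SAP 14. If the sponsor keeps the adverse event tables alone, SAP 14 should at least declare the departure from protocol 12.2.2.

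The cost is some programming on values already graded for the listings, and reported laboratory toxicity rates may be slightly higher. No protocol amendment, subject procedure or dosing rule changes.

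Amending protocol 10.4 is optional and not part of this remedy. It would need IRB/IEC review under protocol 12.5. With the SAP dated January 2021 and data cuts in 2020, sites would have to assign grade and causality retrospectively to any added event.
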